11.5.2 Subset Analyses

The primary endpoint will be presented descriptively for the following subsets in addition they will be entered as additional covariates in the primary efficacy endpoint ANCOVA model to evaluate their effect on the change from baseline HDRS-17 score:

- Age Group (by median age)
- Sex (at birth)
- Baseline HDRS-17 severity (≥ 26 , 20-25, 17-19)
- Baseline Resistance, ATRF 1 vs. 2-4
- Concomitant anti-anxiety medication use, Yes/No
- Concomitant insomnia (includes anti-anxiety medications used to treat insomnia at bedtime) medication use, Yes/No
- Concomitant anticonvulsant medication use, Yes/No
- Comorbidities migraine and pain disorders, Yes/No
- Past history of ECT, TMS or VNS treatment, Yes/No
- Subjects on subtherapeutic dose of antidepressant, Yes/No
- Blinding assessment - The effect of potential unblinding will be evaluated as a sensitivity analysis, where an additional binary variable identifying subjects correctly guessed their treatment assignment versus those who did not will be added to the ANCOVA model as a covariate.

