**Subset Analyses of Primary Endpoint:**

Significant or important variables, such as demographic or other baseline patient characteristics or concomitant medications (depending on use), will be entered as additional covariates in the primary efficacy endpoint ANCOVA model to evaluate their effect on the change from baseline HDRS17 score.

- Use of concomitant medications.
- Blinding assessment
- US vs. OUS sites

The effect of potential unblinding will be evaluated as a sensitivity analysis, where an additional binary variable identifying subjects unblinded versus those not un-blinded will be added to the ANCOVA model as a covariate.

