1. INTRODUCTION

This Statistical Analysis Plan (SAP) is a more detailed companion to the Statistical Methods section of the study titled “The MOOD study – external Combined Occipital and Trigeminal Nerve Stimulation (eCOT-NS) for the treatment of Major Depressive Disorder (MDD)” and provides a comprehensive description of the analysis sets, endpoints, methods, and data analyses to be used. This SAP prevails when differences exist in descriptions or explanations provided in the protocol and the SAP. We shall address analysis strategies for the open label stage of the study. Addressed as well is a plan for prognostic factor analysis to identify potential baseline parameters related to the primary endpoint and its derivatives.

Relivion®DP, an external Combined Occipital and Trigeminal Afferent Stimulation (eCOT-AS) is proposed as a novel treatment for MDD. The combination of neuromodulation of both the occipital and the trigeminal nerve branches non-invasively is made possible for the first time, after having been successfully performed either separately or in invasive procedures.

Major depressive disorder is one of the leading causes of disability worldwide. However, treatment options are still limited, therefore new approaches are needed to enhance clinical improvement. The non-invasive combined neuromodulation of both the occipital and trigeminal nerve branches is a safe, self-administered novel technology with high potential for treating MDD patients. Based on this rationale, Neurorelief developed the Relivion®DP, a neuro-stimulator applying combined occipital and trigeminal afferent stimulation for treatment of major depressive disorder (MDD). Following completion of an early clinical study showing promising results, Neurorelief designed the proposed clinical trial to evaluate the safety and efficacy of the Relivion®DP in a two-arms controlled, double blinded randomized study.

The MOOD Study will evaluate the safety and efficacy of a self-administered treatment for MDD using an external combined occipital and trigeminal afferent stimulator (Relivion®DP).

This pivotal clinical investigation is intended to support future marketing applications (US FDA and CE) for Neurorelief’s Relivion®DP device.

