11.4 Prognostic Factor Analysis

This section is intended to provide the architecture for this evaluation and does not jeopardize the sanctity of this study because this evaluation is being conducted independent of the randomized treatment assignment. Although

randomization creates asymptotic balance in important prognostic factors, including baseline values of the outcome variable in finite samples an imbalance in such factors may occur notwithstanding randomization, this represents the difference between the expectation of a random process and its realization. Depending crucially on the correlation between the baseline covariate and the outcome variable, this chance imbalance may not only create a potential bias in crude estimates of treatment effect in the outcome variable but may also affect the precision with which such an effect is measured and the statistical power of the analysis. Adjustment through the ANCOVA model is recommended to reduce risk of bias whilst also improving the precision of estimates and the power of the statistical test (Egbewale et al. BMC Medical Research Methodology 2014, 14:49). Specifically, if there was a significant difference in the HDRS-17 or in the secondary endpoints response and remission rates detected between the active and sham groups at 8 weeks post treatment initiation, but a retrospective analysis determined that the effect may have been influenced by one or more covariates not defined in the randomization scheme, the conclusion drawn from the unadjusted results could be challenged (Egbewale et al. BMC Medical Research Methodology 2014, 14:49).

The protocol and Statistical Analysis Plan (SAP) are clear regarding the tests for poolability (12.9.6 of the study protocol) and subset analyses (12.9.1 of the study protocol) that should be conducted. From Section 12.9.6 of the study protocol:

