11.5 Endpoints Analyses

11.5.1 Primary Efficacy Endpoint Analyses

The primary efficacy endpoint is the change from baseline to 8 weeks post treatment initiation in HDRS-17 score.

The change in HDRS-17 from baseline to 8 weeks post treatment initiation will be compared between the treatment groups using a repeated measures analysis of covariance (ANCOVA, SAS® MIXED procedure). The model will include the following fixed effects: treatment group, visit, treatment group by visit interaction

with Baseline HDRS-17, and center entered as covariates. If covariates are identified in the prognostic factor analysis, they may be added to the model as well. Baseline HDRS-17 scores will be entered as a continuous variable so that the potential for co-linearity problems will be minimized. The treatment group by center interaction will be evaluated as well, but not as part of the principal statistical evaluation.

The unstructured covariance matrix structure will be used. If the model does not converge, then either the compound symmetry or autoregressive (whichever model has the lower AIC statistic) covariance matrix structure will be used instead. At this time point (up to 8 weeks) we do not expect a high proportion of dropouts, as a placebo effect of the sham treatment is expected and was taken into consideration in the design of the study. Thus, any missing data at 8 weeks post treatment initiation can be considered missing at random. Therefore, since repeated measures ANOVA is also an imputation method, for this evaluation no other method of imputation of missing data is considered beyond the model estimates. Nevertheless, should the missing at random assumption prove to be incorrect, a sensitivity analysis using other methods for data imputation mentioned in Section 7 may be performed.

Mock SAS code for the analysis:

```
Proc Mixed data=HDRS17;
  class visit group center subjectid;
  model change_HDRS17 = baseline_HDRS17 visit group visit*group;
  repeated / type=un subject=subjectid;
  lsmeans group*visit / pdiff cl;
  random center;
run;
```

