11.5.3 Pooling

Subgroup analysis of the primary efficacy endpoint by comparing clinical centers will be used to evaluate the poolability of the results. Treatment by center interaction will be tested in the primary analysis model at a significance level of 10%. This interaction term is not part of the primary endpoint model. If the interaction is found significant the reason for this interaction will be further explored and rationalized. This evaluation may include demographic features, symptoms at presentation, and clinical and treatment history, and center comparability in the features found to be associated with the primary efficacy variable.

In the case that poolability is questionable, the reasons for differential treatment effect, such as subject and clinical characteristics, will be investigated and reported.

11.5.4 Secondary Efficacy Endpoint Analyses:

- Proportion of responder subjects- defined as the percent of subjects achieving at least 50% reduction from baseline in their HDRS-17 total score, 8 weeks post Relivion®DP treatment initiation - will be summarized by a count and percentage and compared between the groups with a chi-squared test and a Fisher's exact test. The odds ratio with 95% Wald confidence interval will be presented as well. As an additional measure of effect size the NNT will be presented. If covariates are identified in the prognostic factor analysis, logistic regression will be performed as well adjusting for the identified factors.
- Proportion of subjects achieving remission- defined as the percent of subjects with HDRS-17 score≤7 at 8 weeks post Relivion®DP treatment initiation- will be summarized by a count and percentage and compared between the groups with a chi-squared test and a Fisher's exact test. The odds ratio with 95% Wald confidence interval will be presented as well. As an additional measure of effect size the NNT will be presented. If covariates are identified in the prognostic factor analysis logistic regression will be performed as well adjusting for the identified factors.

- Mean change in depressive symptoms, measured by MADRS total score, from baseline to week-8 post treatment initiation - will be compared between the groups using a similar model as the primary endpoint.

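### The subset model in SAP 11.5.2 has no treatment-by-subset term, so it estimates prognosis and cannot formally assess whether the device effect differs by subset

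*SAP*

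**What the plan says.** SAP 11.5.2 lists eleven variables: age group, sex, baseline HDRS-17 severity band, ATRF level, three kinds of concomitant medication, migraine and pain comorbidity, past ECT/TMS/VNS, subtherapeutic antidepressant dose, and whether the subject guessed the assignment correctly. It plans two things for them. First: "The primary endpoint will be presented descriptively for the following subsets". Second, in addition, "they will be entered as additional covariates in the primary efficacy endpoint ANCOVA model to evaluate their effect on the change" from baseline in HDRS-17.

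The subset paragraph of Protocol 12.9.1 has the second step only, for a shorter list. Its variables "will be entered as additional covariates in the primary efficacy endpoint ANCOVA model to evaluate their effect on the change from baseline".

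The model that receives these covariates is given as mock code in SAP 11.5.1: "model change_HDRS17 = baseline_HDRS17 visit group visit*group", with center as a random effect. Its only interaction is visit by group.

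The one treatment interaction that the SAP's own analysis sections specify is in 11.5.3: "Treatment by center interaction will be tested in the primary analysis model at a significance level of 10" per cent. Center is not an 11.5.2 subset. Protocol 12.9.1 repeats the center analyses for US versus outside US, which is not in the 11.5.2 list either. The prognostic factor analysis in SAP 11.4 gives no treatment comparison, since "this evaluation is being conducted independent of the randomized treatment assignment". Where the two documents differ, the SAP governs: "This SAP prevails when differences exist in descriptions or explanations provided in the protocol and the SAP".

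**The concern.** A subset analysis of a randomised comparison is normally read as asking whether the treatment difference is consistent across kinds of patient. A covariate main effect answers another question: whether patients at one level improve more or less than patients at another, whichever arm they are in.

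Two things are at stake. In a pivotal study meant to support marketing applications, consistency across severity, treatment resistance, sex and prior stimulation would have no adjusted estimate and no interval. And a significant covariate, reported under the heading of subset analyses, could be taken for a subset-specific device effect when it shows only prognosis.

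**Working it through.** **1. The algebra.** Let G be the arm, V the visit and S a two-level subset variable. The planned model is

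change = baseline + V + G + V×G + βS.

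The week-8 treatment difference is the G term plus the V×G term at week 8. S does not appear in it, so the fitted difference is the same at both levels. β is also common to weeks 4 and 8, because no S×V term is named. If γ(G×S) is added, the difference becomes δ at S=0 and δ+γ at S=1. The quantity of interest is γ, and the planned model does not contain it.

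**2. The plan's own sample size.** Inputs from Protocol 12.4: difference 3.3, SD 6, two-sided 5%, 80% power.
- Normal approximation: n = 2 × (6 × (1.960 + 0.842)/3.3)² = 51.9, so 52 per arm.
- Exact t-test: 53 per arm, power 80.1%.

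The stated 53 per arm (106 in total) reproduces.

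**3. What the covariate responds to.** I used 5,000 simulated trials of 106 subjects, 53 per arm, with a subset split in half, normal errors of SD 6 and one post-baseline time point. The effect patterns are chosen to isolate the mechanism and are not predictions.

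| True situation | Covariate p<0.05 | Treatment×subset p<0.05 |
|---|---|---|
| Device effect 0 in one half, 6.6 in the other, equal mean outcome | 4.1% | 80.6% |
| Factor purely prognostic (3.3 points), device effect 3.3 throughout | 80.2% | 5.4% |
| Neither | 4.7% | 5.4% |

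In the first row the main-effects model returns a mean treatment difference of 3.28 for everyone, and its covariate is significant at chance level only.

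**4. What an added interaction would deliver.** For a subset of share f, SE(γ) = 6 × √(4/(106f) + 4/(106(1−f))). Shares are assumptions, because the documents give none.

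| Split | SE (points) | Power for 3.3 points, two-sided 5% | Power at 10% | Detectable with 80% power at 5% |
|---|---|---|---|---|
| 50/50 | 2.33 | 29% | 41% | 6.5 |
| 30/70 | 2.54 | 25% | 36% | 7.1 |
| 20/80 | 2.91 | 20% | 30% | 8.2 |

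For 80% power on a 3.3-point interaction with a 50/50 split, the total is N = 16 × (6 × 2.802/3.3)² = 415.1, so 416 evaluable subjects. With a 50/50 split, the difference within one level has SE 6 × √(4/53) = 1.65 and a 95% half-width of about 3.2 points.

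**5. Multiplicity.** Ten of the eleven variables remain once correct guess is set aside. If the ten tests were independent at 5%, the chance of at least one false positive would be 1 − 0.95¹⁰ = 40%.

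**6. Why correct guess is different.** It is defined from the arm. Assume a two-option guess, and let B be belief in active treatment. Correct guess is then B in the active arm and 1 − B in the sham arm. If belief improves scores, the slopes on correct guess run in opposite directions in the two arms and tend to cancel in a main effect. Treatment by correct-guess is merely a recoding of belief, not a subgroup effect. Protocol 9.1.2 also places the blinding questionnaire after randomisation and device practice.

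**The case against.** The strongest reply is that the method fits the aim as written. Both documents say that the covariates are entered to evaluate their effect on the change score. That is a prognostic question, and a main effect answers it. No objective, endpoint, success criterion or claim depends on effect modification. This stands: the documents do not break a promise to test heterogeneity, and the point is an improvement rather than the correction of an error.

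A reader might infer that heterogeneity would leave no sign at all in the results. The documents do not support that. The same sentence of SAP 11.5.2 plans descriptive presentation by subset, and tables split by arm would let a reader see raw differences. What is missing is a statement that they will be by arm, and any adjusted difference, interval or interaction estimate.

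A reader might also infer that the covariate step only duplicates SAP 11.4. That is partly true. Age, sex, ATRF and baseline HDRS are in both lists, and the severity bands come on top of continuous baseline HDRS-17. But 11.4 does not list anti-anxiety, insomnia or anticonvulsant medication, migraine and pain comorbidity, subtherapeutic dose or the guess, and it is univariate without treatment.

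SAP 11.5.3 does provide for investigating reasons for a differential treatment effect, but only if poolability across centers is questionable. Finally, the low power in the working is a fair objection to any claim from these analyses. It is not an objection to reporting estimates with intervals.

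**Conclusion.** The point holds as a low-severity improvement. As specified, the subset model gives one common treatment difference and a prognostic coefficient for each variable. It cannot formally assess whether the device effect differs by subset, and the descriptive part does not fill that gap.

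That the variables enter as main effects only is inferred from their description as additional covariates and from the mock code. Nothing in either document contradicts it. The precision figures rest on 106 evaluable subjects, SD 6, two-level subsets and assumed shares. The three-band severity variable needs two interaction contrasts, and the repeated-measures model may be somewhat more precise than these single-visit figures.

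The primary analysis and its conclusion are untouched. It would also be wrong to conclude that every listed variable should get an interaction. Correct guess is known only after randomisation. Protocol 9.7 provides for use of some anti-anxiety and insomnia drugs during the double-blind phase. A device effect within levels of a post-randomisation variable is not a randomised comparison.

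**What to change.** In SAP 11.5.2:
- Limit the subset step to variables defined at or before randomisation: age group, sex, baseline HDRS-17 severity, ATRF level, concomitant medication use at baseline, comorbidity, prior ECT/TMS/VNS, and subtherapeutic dose at baseline. State that the medication and dose variables are classified at baseline.
- For each, one at a time, fit treatment by subset and treatment by subset by visit with their lower-order terms. Report the week-8 LS mean difference with 95% CI at each level, and the week-8 interaction estimate with its CI.
- State that the descriptive tables are by arm.
- Label all of this exploratory, with no claim resting on it.
- Move correct guess and post-randomisation medication use to separate sensitivity analyses.

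The cost is about ten further models on data already collected. The price in interpretation is wide intervals, low power and multiplicity across about ten variables, and rare levels may be too sparse to read. SAP section 6 says that the treatment code was not revealed up to SAP finalisation. If it has since been broken, the addition should be labelled post hoc.

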## 7.4. Measures to Minimize Bias

Several measures will be implemented to minimize systematic error/bias:

- Randomization to active treatment vs. sham control.
- Blinding of both study subjects, site study personnel and efficacy outcome measure raters.
- Subjects will be asked for their opinion concerning their group assignment. Their response will be documented in the CRF.
- Depression severity and symptoms would be assessed according to the HDRS/MDRS and additional assessment tools by a qualified blinded rater, with an attempt for one rater to evaluate same subject through study visits.
- Study dedicated central trainer/technical support person would be blinded to the efficacy outcome measure scores throughout the study.
- Study subjects will be instructed not to disclose any details of the treatment sessions to the study blinded raters during rating sessions.
- Study subjects will be instructed to report all adverse events to the clinical site team or the central device trainer/technical support but not to the blinded study rater.
- Screening log will be completed by investigational sites listing all major depression patients consented to the MOOD study. The log will include reasons for exclusion from the study.
- Reported serious adverse events and device related adverse events will be reviewed and adjudicated, if required, by Neurolief and if needed forwarded to the study 'Data Monitoring Committee' (DMC) for further review and assessment. The adjudicated results will be updated in the study CRF and used in all cases for purposes of data analysis.
- The sponsor, the DMC and Principal Investigators will oversee the overall safety of the study. The DMC will periodically review safety data and will make recommendations concerning continuation, modification, or termination of the study.
- Clinical monitors will verify patients' data and ensure compliance with good clinical practice (GCP), CIP and other study requirements.

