### **9.1.2. Visit 2 – Baseline (Day -4 - 0) Eligibility evaluation, Randomization and device training.**

Written below are the assessments to be completed at Visit 2 (either on site or remotely):

- Eligibility assessment.
- PRO training for subjects self-reported questionnaire (QIDS-SR-16 and Q-LES-Q) (hard copy and/or electronic)
- Depression symptoms questionnaires:
  - By site qualified rater: HDRS21 (HDRS17- removing 4 last questions from the HDRS21), MDRS, CGI-S & CGI-I
  - By subject: QIDS-SR-16, Q-LES-Q. Subject self-reported questionnaire may be filled in electronically (ePRO) or by hard copy
- Document change in antidepressant medication, if any.
- Documented significant change in health status, if any.
- Suicidal intent assessment by the investigator team (C-SSRS).
- A review the study requirements with the subject to help ensure compliance.
- Randomization to Active Treatment or Sham Control.
- Subject will be provided with the device and the cellular app installed either on their personal iPhone or on a dedicated study iPhone, as applicable. Device and cellular iPhone, if required, may be provided to the subject at the site (in the case of an on-site visit) or by delivery (in the case of a remote visit)
- Device training will be performed by the study central trainer and may be performed during an on-site visit or in a remote fashion.

 Neurolief Brain Innovation	MOOD: CLINICAL INVESTIGATION PLAN	Doc No.: CL-CIP-201 Rev: REV.3 / 09June2021 Pg. 47 of 92
--	--	--

- Subject will read the User manual, the quick guide and will watch the instructional video and be trained on the device and recommended treatment regimen (detailed on the Relivion®DP Quick guide) by the study central trainer (on-site or remote).
- Device size will be adjusted to subject head circumferences.
- Subject will self-practice the device along with the mobile application to become familiar with its use and with the stimulation sensation.
- Blinding Assessment questionnaire (by hard copy or electronically (ePRO)
- Adverse events occurring during the visit will be documented.

Study visit 2 may occur in between study day -4 to study day 0 to allow for a device shipment to subject home and a remote device training. In any case, the day of the device training would be considered as study day 0.

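### Adjusting for a correct guess of treatment arm cannot show how far unblinding drives the HDRS-17 result, and can enlarge the bias

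*SAP*

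**What the plan says.** SAP 11.5.2 states the aim: "The effect of potential unblinding will be evaluated as a sensitivity analysis". The method is one binary covariate in the primary ANCOVA, "identifying subjects correctly guessed their treatment assignment versus those who did not will be added to the ANCOVA model as a covariate". The same section also presents the primary endpoint descriptively for each listed subset, and blinding assessment is on the list.

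Protocol 12.9.1 (Subset Analyses of Primary Endpoint) is less specific: "an additional binary variable identifying subjects unblinded versus those not un-blinded will be added to the ANCOVA model as a covariate". It does not define unblinded. SAP section 1 settles precedence: "This SAP prevails when differences exist in descriptions or explanations provided in the protocol and the SAP". The correct-guess definition therefore governs.

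The data come from the subject. Protocol 7.4 says "Subjects will be asked for their opinion concerning their group assignment". Protocol 9.1.2 lists the "Blinding Assessment questionnaire (by hard copy or electronically (ePRO" item after the subject's device practice, and Table 1 marks the questionnaire at Visit 2 only. The documents specify no blinding index, no analysis by the guess itself and no rule for an undecided answer.

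**The concern.** In a sham-device trial the worry is that a subject who believes the device is active reports more improvement whatever the device does. The variable that carries this is the perceived assignment. A correct guess is a different quantity: it means belief in active in one arm and belief in sham in the other. Adjusting for it groups active subjects who expect benefit with sham subjects who expect none, and within that group belief and arm cannot be told apart.

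The risk is plausible here. Protocol 6.3.1 sets sham at 0.33 Hz, falling to 0.2 mA after 3 minutes, against 80 Hz for active, and Protocol 6.8 has users raise the intensity until they feel tingling. What is at stake is interpretation. An adjusted estimate that matches the unadjusted one could be reported as showing that unblinding did not drive the result, when the match follows from how the covariate is built.

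**Working it through.** **Scale from the plan.** The documents give no figure for this analysis. The design inputs (Protocol 12.4) are a difference of 3.3 points, SD 6 and 53 per group. They reproduce: the two-sided 5% t-test has 80.1% power at 53 per group and 79.3% at 52. I use 3.3 points only as an assumed size for a belief effect.

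**Set-up.** The primary model is "model change_HDRS17 = baseline_HDRS17 visit group visit*group" with unstructured covariance and random center. Let T = 1 for active, G = 1 for guessed active, and C = 1 for a correct guess. Then C = TG + (1−T)(1−G). Let t be the device effect and b the extra improvement from believing one is on active, both in points of HDRS-17 reduction and additive. Allocation is 1:1. Let qa and qs be the shares guessing correctly on active and sham.

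**Unadjusted.** Believers make up qa of active and 1−qs of sham, so the expected difference is t + b(qa + qs − 1).

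**Adjusted for C.**
- Correct guessers: active subjects believe active and sham subjects believe sham, so the arm difference is t + b.
- Incorrect guessers: the reverse holds, so it is t − b.
- The adjusted estimate averages these with weights w1 = qa·qs/(qa+qs) and w0 = (1−qa)(1−qs)/(2−qa−qs), giving t + b(w1−w0)/(w1+w0).

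**Equal rates, qa = qs = q.** Here w1 = q/2 and w0 = (1−q)/2, so the adjusted value is t + b(2q−1), the same as the unadjusted one. C is uncorrelated with T, so adjustment moves nothing.

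**Unequal rates, qa = 0.9 and qs = 0.3.** Unadjusted bias: 0.9 + 0.3 − 1 = 0.20b. Weights: w1 = 0.27/1.2 = 0.225 and w0 = 0.07/0.8 = 0.0875. Adjusted bias: (0.225 − 0.0875)/(0.225 + 0.0875) = 0.1375/0.3125 = 0.44b.

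**Adjusted for G.** Within each guess stratum belief is the same in both arms, so the difference is t and no bias remains.

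Bias as a multiple of b:

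| Correct, active/sham | Unadjusted | Adjusted for C | Adjusted for G |
|---|---|---|---|
| 70/70% | 0.40 | 0.40 | 0 |
| 80/80% | 0.60 | 0.60 | 0 |
| 90/90% | 0.80 | 0.80 | 0 |
| 100/100% | 1.00 | 1.00 (C constant) | not estimable (G = T) |
| 90/30% | 0.20 | 0.44 | 0 |

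With b = 3.3 and no device effect, the 70, 80 and 90% rows come to 1.32, 1.98 and 2.64 points, and the last row goes from 0.66 to 1.45. A simulation of 200,000 subjects at a single time point agrees. It gives 1.31, 1.96 and 2.70, unchanged by adjusting for C, and 0.62 rising to 1.41 in the unequal case. Adjusting for G leaves about 0 (within 0.06) in all four.

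**Precision.** If a share g guesses active in both arms, corr(C,T) = 2g−1. At a single time point the SE multiplier is 1/√(1−(2g−1)²): 1.25 at g = 0.8 and 1.67 at g = 0.9. In the planned two-visit model, with C as a main effect and an assumed within-subject correlation of 0.3 to 0.7, the week-8 multiplier is 1.17–1.22 and 1.47–1.59. At g = 0.6 even the single-time-point figure is only 1.02. For G, the correlation with arm is 2q−1 when a share q is correct in each arm, so the same multipliers apply at 80% and 90% correct.

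**The case against.** **The descriptive output helps.** SAP 11.5.2 also calls for a descriptive presentation by subset. Under complete unblinding the incorrect group would be empty, and a reader would see it. If the table is split by arm and the answer is yes/no, guess by arm can be recovered from it. This stands. A reader might infer that the plan cannot reveal unblinding at all, or that a check is passed when blinding fails. The documents support neither: the table would reveal it, and no pass/fail rule is attached. The defect lies in the adjusted estimate.

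**Loss of precision is not peculiar to this covariate.** A reader might infer that it uniquely inflates the treatment SE and could produce a spurious loss of effect. That does not stand. Perceived assignment has the same multipliers when guesses track the arm. When the same share guesses active in both arms, w1 = w0 and the estimate is unbiased; only its interval widens. The size depends on a guess share the documents do not give, and the analysis has no power target.

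**Complete unblinding defeats any covariate.** This is true. The difference is that perceived assignment then fails visibly, while the correct-guess model returns the unadjusted answer.

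**The protocol wording is different.** Protocol 12.9.1 does not tie unblinded to guesses and could refer to code breaks, which Protocol 9.6.2 allows. The algebra is therefore a criticism of the SAP definition only.

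**Raters are blinded.** Protocol 7.4 tells subjects not to describe sessions to the rater. That limits rater bias, but does not stop a subject's own belief from affecting what is reported.

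**Conclusion.** The point holds for the adjusted analysis in SAP 11.5.2. With equal correct-guess rates in both arms the covariate removes none of a belief effect, and at 90% and 30% correct it more than doubles the bias, from 0.20b to 0.44b. An unchanged estimate is therefore not evidence of robustness.

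This rests on additive device and belief effects and a two-option guess. In a finite sample, equality of the adjusted and unadjusted estimates is exact only when C is balanced over arms and the other covariates. The direction of the finding does not depend on the assumed 3.3 points; the guess rates are illustrative.

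A reader might infer that the trial's main conclusion is at risk. It is not: the primary test, sample size and success rule do not use this variable. The consequence is a sensitivity analysis that cannot do its stated job.

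**What to change.** In SAP 11.5.2:

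1. Replace the correct-guess covariate with perceived assignment: guessed active, guessed sham, and do not know if the questionnaire offered that option. The response options are not in the documents.
2. Tabulate guess by arm and report a blinding index for each arm.
3. Show the week-8 HDRS-17 treatment difference, with confidence interval, within each guess stratum.
4. State the limits. Precision falls as guesses track the arm, and the adjusted effect cannot be estimated if every guess is correct. The guess is made after randomization, so the strata are not randomized comparisons. It is scheduled at Visit 2 only, so belief that develops over the 8 weeks is missed.
5. Say what unblinded means in Protocol 12.9.1, and report any code breaks separately.

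The cost is SAP wording and a few tables from data already scheduled. SAP section 6 says the treatment code had not been revealed when the SAP was finalized. If it has been since, report items 1 to 3 as labelled supplementary analyses, and do not present the correct-guess result as evidence of robustness.
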